8.11 Unscheduled Visit

At the Investigator's discretion, an Unscheduled Visit may be completed at any time during the study, but prior to the SFU Visit, if deemed necessary for the subject's safety and well-being.

If an additional visit (or unscheduled visit) is conducted due to safety or efficacy reasons, an eC-SSRS assessment will be performed with the subject during the visit. If an additional visit (or

unscheduled visit) is conducted for reasons other than safety or efficacy concerns (eg, replacement of lost medication, repeated collection of a laboratory specimen due to collection or analysis issues), an eC-SSRS will not be required at these visits.

At this visit, any of the following assessments may be performed, depending on the reason for the visit:

- Vital signs
- Physical examination
- Record 12-lead ECG
- eC-SSRS
- If medically indicated, obtain blood sample(s) for:
 - Standard safety laboratory tests (hematology and biochemistry)
 - The blood sample may also be used for PK assessments, if needed
- Obtain urine sample for standard safety laboratory tests (urinalysis; including urine pregnancy test)
- Concomitant medications
- Record AEs

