9.1.2 Procedures for reporting and recording AEs

The subject will be given the opportunity to report AEs spontaneously. A general prompt will also be given at each study visit to detect AEs. For example:

“Did you notice anything unusual about your health (since your last visit)?”

In addition, the Investigator should review any self-assessment procedures employed in the study.

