2.2 Study variable(s)

2.2.1 Safety variables

2.2.1.1 Primary safety variable

The primary safety variable is the incidence of treatment-emergent adverse events (TEAEs) adjusted by duration of subject exposure to treatment.

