4.3 Interim analyses and data monitoring

When PS0010 is unblinded, Sponsor study team members from PS0011 with access to the PS0010 data will be unblinded. However, subjects and investigators will remain blinded. This operational unblinding to PS0011 treatment assignment will pertain to selected clinical PS0010 study team members (some of whom may be involved in PS0011). PS0010 and PS0011 will have the same blinded programming teams for reporting and will remain blinded to PS0010 and PS0011 treatment assignment. An independent programming team will be used for the final unblinding for PS0010 reporting.

A Data Monitoring Committee (DMC) will review the safety data on a recurring basis as outlined in the DMC charter. The outputs reviewed by the DMC will include the accrued data from both PS0010 and PS0011, allowing for summaries of the combined data across the studies. The details of the outputs to be prepared are described in a separate DMC SAP.

An interim analysis focusing on PS0011 only will take place once all subjects have completed the Week 48 visit, but not including the SFU visit. The Clinical Study Report will be updated at a later date in order to incorporate the SFU data once available.

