8.1.3 Derivation of exposure at risk

Throughout this section, date of last clinical contact for each subject is defined as the maximum of [last visit date including SFU visits, last imputed AE start date, date of study termination or completion, last date of study drug administration].

In general, exposure days at risk will be calculated as:

$$\begin{aligned} \text{Exposure days at risk} \\ = \text{Date of last dose in PS0011} - \text{Date of first dose in PS0011} + 140 \end{aligned} \quad (7)$$

Alternatively, for subjects who die or are lost to follow-up prior to the Week 48 visit, total exposure days at risk will be calculated as:

$$\begin{aligned} \text{Exposure days at risk} \\ = \text{Date of last clinical contact in PS0011} - \text{Date of first dose in PS0011} \\ + 1 \end{aligned} \quad (8)$$

For the analysis based on data through to the last Week 48 visit (see [Section 4.3](#)), there may be subjects who are still ongoing in the SFU period at the time of data cut-off. For such subjects, exposure days at risk will be calculated as follows:

$$\text{Exposure days at risk} = \text{Data cutoff date} - \text{Date of first dose in PS0011} + 1 \quad (9)$$

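### In the Week 48 analysis, SAP equation (9) counts time at risk to the data cut-off although the last scheduled AE prompt was at Week 48 or Early Withdrawal, so EAER and the EAIR of uncommon non-serious TEAEs are biased downward in the first report

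*SAP*

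**What the plan says.** SAP 2.2.1.1 defines the outcome: "The primary safety variable is the incidence of treatment-emergent adverse events (TEAEs) adjusted by duration of subject exposure to treatment". SAP 8.1.6 reports it as EAIR with a 95% confidence interval, together with EAER.

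SAP 4.3 plans an analysis of PS0011 "once all subjects have completed the Week 48 visit, but not including the SFU visit". It adds: "The Clinical Study Report will be updated at a later date in order to incorporate the SFU data once available".

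SAP 8.1.3 has three rules for days at risk:

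- Equation (7), the general rule: last dose minus first dose, plus 140.
- Equation (8), "for subjects who die or are lost to follow-up prior to the Week 48 visit": last clinical contact minus first dose, plus 1.
- Equation (9), for the Week 48 analysis, where "there may be subjects who are still ongoing in the SFU period at the time of data cut-off": cut-off date minus first dose, plus 1.

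Under SAP 8.1.4 an event-free subject brings all of this time into the EAIR denominator. Under SAP 8.1.5 every subject's full time enters the EAER denominator.

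On collection, Protocol 9.1.2 says: "A general prompt will also be given at each study visit to detect AEs". Protocol Table 5-1 and Sections 8.8 and 8.9 place no visit between Week 48/Early Withdrawal and SFU. Two other routes exist. Protocol 9.1.2 also says "The subject will be given the opportunity to report AEs spontaneously", and under Protocol 8.11, at the Investigator's discretion, "an Unscheduled Visit may be completed at any time during the study, but prior to the SFU Visit".

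**The concern.** A rate per subject-year needs events and time observed over the same interval. For subjects waiting for SFU, equation (9) runs the denominator to the cut-off, while systematic questioning about AEs stopped at Week 48 or Early Withdrawal. Non-serious events from the gap will mostly surface at the SFU visit, after this analysis. The SAP applies the matching principle in equation (8), but only to deaths and losses before Week 48.

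Protocol 14.2 plans no inferential analysis, so the rates per 100 subject-years are themselves the primary result. A denominator that is too large lowers the estimate and its confidence interval together. The effect also depends on when a subject entered relative to the cut-off, which has nothing to do with safety.

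**Working it through.** **Inputs from the documents.** 24 expected injections, two per dose (SAP 7); SFU visit 140 days after the last dose; maximum duration 64 weeks (Protocol 5.1.1); up to 240 subjects (Protocol 5.1.2). **Assumed:** uniform entry over W weeks, cut-off at the last Week 48 visit, no early withdrawals. The documents give neither the entry period nor the cut-off date.

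**1. Reproduce the stated duration.** 24 / 2 = 12 doses, at Weeks 0 to 44. 44 + 20 = 64 weeks, as stated. Equation (7) gives 308 + 140 = 448 days = 64 weeks. (Protocol 5.1 refers to administration through Week 48, and the dosing row of Table 5-1 appears to include it, while Section 8.8 lists no dose. These passages must be reconciled; a last dose at Week 48 would make the gap below 140 days.)

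**2. Gap per completer.** Week 48 is day 336, so the longest gap is 448 − 336 = 112 days, and 112/448 = 25%. The +7-day SFU window makes it 119.

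**3. One event-free subject.** Time to the last prompt is 336 + 1 = 337 days. Gaps of 28, 56, 84 and 112 days are credited as 365, 393, 421 and 449 days. The ratios 337/365 and so on are 92%, 86%, 80% and 75%.

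**4. Whole trial, EAER or EAIR of a rare event.** For W of 16 or more, a fraction 16/W is still in SFU at cut-off, with a mean gap of 8 weeks. The rest have 64 weeks, with their SFU data taken as included.

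- Mean credited weeks: 64 − 8 × 16/W = 64 − 128/W
- Mean weeks to last prompt: 64 − 16 × 16/W = 64 − 256/W

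For W = 26: 54.15/59.08 = 0.917. Subject-years are 240 × weeks/52.18. If half of the gap events are captured, the numerator is the prompted time plus half the gap.

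**5. A common endpoint.** EAIR stops each subject's clock at the first event. Take 1.5 first events per subject-year for any TEAE (assumed), or 0.02875 per week. For W = 16, the proportion with an event by Week 48 is 1 − exp(−1.38) = 0.748. Time to first event averages 0.748/0.02875 = 26.0 weeks, and equation (9) adds 0.252 × 8 = 2.0 weeks. The ratio is 26.0/28.0, about 0.93.

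| W (weeks) | In SFU, of 240 | Credited SY | SY to last prompt | Ratio | Shortfall, none captured | Shortfall, half captured | EAIR shortfall, any TEAE, none captured |
|---|---|---|---|---|---|---|---|
| 16 | 240 | 257.6 | 220.8 | 0.857 | 14% | 7% | 7% |
| 26 | 148 | 271.7 | 249.1 | 0.917 | 8% | 4% | 4% |
| 39 | 98 | 279.3 | 264.2 | 0.946 | 5% | 3% | 3% |
| 52 | 74 | 283.0 | 271.7 | 0.960 | 4% | 2% | 2% |

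**6. If SFU data are left out for everyone.** If subjects past SFU keep the 140 days of equation (7) but their SFU data are not in the cut, the ratio is 48/(64 − 128/W). The shortfall is then 14%, 19%, 21% and 22% for the same four periods.

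**The case against.** The strongest case is that the effect is small, temporary and descriptive. Capture in the gap is not nil: subjects can report spontaneously, unscheduled visits are possible, known AEs are followed up, and sites must pass SAEs on within 24 hours of learning of them. The report will be updated with SFU data, no test or decision rule uses the interim rates, and the same rule applies to every dose group. Protocol 14.3.1 adds 140 days for all subjects except deaths, so equation (9) already credits less unobserved time than the protocol would. All of this limits the size and duration of the bias. None of it changes the direction for non-serious events.

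Three stronger readings are tempting, and the documents do not support them:

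- *The first report's rates are a quarter too low.* The 25% is the maximum for one completer. Trial-level figures depend on an entry period that is not stated, and SAE rates should move little.
- *Rates will rise at the update for no medical reason.* That also depends on the event rate off drug during SFU, which is unknown.
- *SAP 4.3 drops the SFU data of subjects who have finished SFU, so the shortfall is about 19% or more.* The wording may only mean that the analysis does not wait for SFU. SAP 8.1.3 counts SFU visits as clinical contact and has a special rule only for subjects still in SFU, which fits the milder reading. The text is ambiguous, and what it needs is clarification.

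**Conclusion.** The point holds for the first report. Equation (9) adds time without a scheduled AE prompt, and EAER and the EAIR of uncommon non-serious TEAEs are biased downward. With nothing captured in the gap and no early withdrawals, the shortfall is about 14% to 4% for entry periods of 16 to 52 weeks. It halves with half capture, is about 7% to 2% for the EAIR of any TEAE at the assumed rate, and is small for SAEs. For early withdrawals the gap starts at the Early Withdrawal visit; they are not modelled here. The direction follows from the documents, but the percentages are scenarios. The point is worth correcting because these rates are the primary result and the edit is short.

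**What to change.** For the Week 48 analysis, end equation (9) at the last scheduled visit with an AE assessment on or before the cut-off (Week 48 or Early Withdrawal), capped at last dose + 140 days. Count TEAEs in the rates only up to that date, and list later events separately so that no SAE is lost from view.

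Do not substitute the date of last clinical contact from the same section. It is a maximum that includes AE start dates and any unscheduled visit, so time after Week 48 would be kept mainly for subjects with events. An SAE reported promptly after Week 48 would stay in the numerator while most other subjects' time was removed. In the 16-week scenario this overstates a rare SAE rate by about 257.6/220.8 − 1 = 17%.

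State in SAP 4.3 whether SFU data of subjects who have finished SFU are in the cut. If they are not, give those subjects the same end date instead of equation (7).

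The cost is a short SAP edit and slightly less favourable interim rates. Those rates will cover less of the 140-day window, which a footnote should say.

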8.1.4 Derivation of EAIR

The exposure adjusted incidence rate (EAIR) is defined as the number of subjects (n) with a specific AE adjusted for the exposure and will be scaled to 100 subject-years:

$$\text{EAIR} = 100n / \sum_{i=1}^N T_{Exp(i)} \quad (10)$$

where the numerator is the total number of subjects experiencing the AE and the denominator is the total time at risk scaled to 100 subject-years; that is, the total summation of individual subject-years at risk up to the first occurrence of the AE for subjects with that AE, and the total subject-years at risk for those subjects not experiencing that AE, divided by 100.

If a subject has multiple events, the time of exposure is calculated to the first occurrence of the AE being considered. If a subject has no events, the total time at risk is used as defined in [Section 8.1.3](#).

Exact Poisson 95% confidence intervals for incidence rates are calculated using the relationship between the Poisson and the Chi-square distribution (Ulm, 1990):

$$\text{LCL} = \chi^2_{2n, \alpha/2} / 2 \quad (11)$$

$$\text{UCL} = \chi^2_{2(n+1), 1-\alpha/2} / 2 \quad (12)$$

where n is the number of subjects with a specific AE for the incidence rate of interest and is the basis for the number of degrees of freedom for the chi-square quantile for the upper tail probability χ^2 .

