14.3.1 Primary safety analysis

All TEAEs will be summarized descriptively by PS0011 treatment group, primary SOC, high level term (HLT), and preferred term (PT). This summary will include the exposure adjusted incidence rate (EAIR) with associated 95% confidence interval and the exposure adjusted event rate (EAER).

For EAIR, the numerator will be the total number of subjects experiencing the AE. The denominator will be 100 subject-years; that is, the total summation of individual subject-years at risk up to the first occurrence of the AE for subjects with that AE, and the total subject-years at risk for those subjects not experiencing that AE, divided by 100. Exposure adjusted incidence rates will be presented with a 95% exact confidence interval based upon the Chi-Square distribution (Ulm, 1990).

For EAERs, the numerator will be the number of AEs including repeat occurrences in individual subjects; the denominator will be 100 subject-years. That is, the total summation of individual subject-years at risk divided by 100. No confidence interval will be computed for EAER.

Patient exposure at risk in days will be defined as date of last administration of study medication – date of first administration of study medication in PS0011 + 140 days (ie, the duration of the SFU Period). If a subject dies, patient exposure at risk is censored at the date of death. The sum of these exposure days at risk across subjects is converted to years for the EAIR and EAER calculations described above.

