8.1.6 Analysis of the primary safety variable

All TEAEs will be summarized descriptively by PS0011 treatment group, primary SOC, HLT, and PT. This summary will include the number and percentage of subjects experiencing the event, the number of events, EAIR with associated 95% confidence interval based upon the Chi-Square distribution (Ulm, 1990), and the EAER.

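### The SAP's 95% limits for the primary EAIR are limits for a count, not a rate per 100 subject-years, so a printed interval can exclude its own estimate

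*SAP*

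**What the plan says.** Protocol 14.3.1 makes the EAIR of TEAEs the primary safety analysis and asks for an interval on it: "Exposure adjusted incidence rates will be presented with a 95% exact confidence interval based upon the Chi-Square distribution". It gives no formula for the limits.

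SAP 8.1.4 supplies the formulas. Equation (10) sets the EAIR to 100n over the summed time at risk, so it is a rate per 100 subject-years. The section continues: "Exact Poisson 95% confidence intervals for incidence rates are calculated using the relationship between the Poisson and the Chi-square distribution". Equation (11) gives the lower limit as half the chi-square quantile with 2n degrees of freedom at α/2. Equation (12) gives the upper limit as half the chi-square quantile with 2(n+1) degrees of freedom at 1−α/2. The section explains that "n is the number of subjects with a specific AE for the incidence rate of interest" and that this number "is the basis for the number of degrees of freedom for the chi-square quantile for the upper tail probability".

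SAP 8.1.6 then puts "EAIR with associated 95% confidence interval based upon the Chi-Square distribution" in the primary safety table. SAP 8.1.5 gives the EAER no interval.

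**The concern.** The estimate and its limits are on different scales. Equation (10) divides by exposure and multiplies by 100; equations (11) and (12) do neither. Two treatment groups with equal n but tenfold different exposure would have EAIRs tenfold apart and identical printed limits.

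The study plans no inferential tests (Protocol 14.2), and SAP 8.1.6 attaches an interval to no other measure in the primary table. The EAIR interval is therefore the only stated measure of uncertainty for the primary variable. The treatment groups will differ widely in size, because assignment follows the PS0010 dose and PASI90 response. A comparison of groups is where an interval that ignores exposure misleads most.

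The upper-tail wording adds a second problem, since under that reading the lower limit is the larger of the two.

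**Working it through.** The documents print no numerical interval, so there is no figure to reproduce. The check evaluates the formulas directly.

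**Inputs**
- α = 0.05, two-sided and exact (Protocol 14.3.1).
- EAIR = 100n/T, where T is total subject-years at risk (SAP 8.1.4, equation 10).
- Exposure at risk per subject = last dose − first dose + 140 days (SAP 8.1.3, equation 7).
- A completer has 24 injections at two per dose, so 12 doses (SAP 7). Taking the last dose at Week 44: 44 × 7 + 140 = 448 days, and 448/365.25 = 1.227 years.
- Up to 240 subjects (SAP 2.4): 240 × 1.227 ≈ 294.4 subject-years. Forty completers give about 49.1.
- The documents give no observed T or group sizes. The T values below are assumptions, and they ignore early withdrawal and truncation at first AE.

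**Step 1: what equations (11) and (12) estimate.** For n = 1, 2, 5, 10, 20, 40 and 100, the Poisson tail probabilities P(X ≥ n | LCL) and P(X ≤ n | UCL) were both 0.025. The limits are exact for the expected count. Examples: n = 5, 1.62 to 11.67; n = 10, 4.80 to 18.39; n = 20, 12.22 to 30.89.

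**Step 2: limits on the rate scale.** Multiply both by 100/T:

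LCL = 100 × χ²(0.025; 2n)/(2T), UCL = 100 × χ²(0.975; 2(n+1))/(2T).

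The ratio of a limit as written to the correct limit is T/100, so the two agree only at T = 100.

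**Step 3: comparison.**

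| n | T (assumed) | EAIR | As written | Estimate inside? | Scaled by 100/T |
|---|---|---|---|---|---|
| 3 | 19.6 (16 subjects) | 15.29 | 0.62 to 8.77 | no | 3.15 to 44.67 |
| 10 | 25 | 40.0 | 4.80 to 18.39 | no | 19.18 to 73.56 |
| 10 | 150 | 6.67 | 4.80 to 18.39 | yes | 3.20 to 12.26 |
| 10 | 250 | 4.0 | 4.80 to 18.39 | no | 1.92 to 7.36 |
| 20 | 50 | 40.0 | 12.22 to 30.89 | no | 24.43 to 61.78 |
| 20 | 200 | 10.0 | 12.22 to 30.89 | no | 6.11 to 15.44 |
| 20 | 289.5 (236 subjects) | 6.91 | 12.22 to 30.89 | no | 4.22 to 10.67 |

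The rows with n = 10 at T = 25 and T = 250 show the tenfold case. The printed limits are identical, while the correct intervals do not overlap.

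**Step 4: when the estimate falls outside.** This happens when T < 100n/UCL or T > 100n/LCL, using the limits as written:
- n = 1: T < 17.9 or T > 3949.8
- n = 5: T < 42.9 or T > 308.0
- n = 10: T < 54.4 or T > 208.5
- n = 20: T < 64.7 or T > 163.7
- n = 50: T < 75.9 or T > 134.7

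With about 49 subject-years for 40 completers and about 294 for 240, both sides are reachable from n = 10 upwards.

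**Step 5: upper-tail reading.** If the subscripts are upper-tail areas, n = 20 gives LCL = 29.67 and UCL = 13.00. Only lower-tail probabilities put the limits in the right order.

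**Step 6: n = 0.** Equation (11) then has zero degrees of freedom and no lower limit is defined. The convention is 0.

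**The case against.** The intent is clear. Both documents say the interval belongs to the rate, and the cited method paper concerns a standardized mortality ratio, which has a denominator. The chi-square method is correct, and only the final division by exposure is missing. An experienced programmer might add it unprompted, and an interval that excludes its estimate would probably be noticed in output checking. No table or code is available to show that anything has been programmed wrongly. No test or decision rule uses these limits, and the counts, percentages, EAIR and EAER are unaffected.

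For rare preferred terms the estimate usually stays inside even without scaling. The illustrative group sizes (236 and 16) are not in the documents. Truncating time at first AE would also change the figures: if the 20 affected subjects had onset at mid-period, T would fall by 20 × 1.227/2 ≈ 12.3, and the EAIR would move from 6.91 to about 7.2. The upper-tail phrase sits in a garbled sentence and is mainly a wording matter.

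Most of this is fair as to how likely wrong output is. It does not rescue the formulas. Correct results should not depend on someone departing from the stated equations. Output checking would also miss the cases where the estimate happens to lie inside: n = 10 at T = 150 prints 4.80 to 18.39 instead of 3.20 to 12.26, and nothing looks amiss. For rare events the limits are still off by the factor T/100. With n = 1 and T = 294.4, the printed upper limit is 5.57 against a correct 1.89.

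**Conclusion.** The concern holds. Equations (11) and (12) are exact limits for a count, presented as limits for a rate, and nothing elsewhere in the protocol or SAP rescales them. Followed literally, they are wrong by the factor T/100 in every cell where total time at risk is not 100 subject-years. In the larger groups, and in small groups with several events, the interval can miss its own estimate.

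The scale error follows from the formulas alone. Only the worked values rest on the assumed T: 448 days per subject, no early withdrawal and no truncation at first AE. A last dose at Week 48 would raise the ceilings from 49.1 and 294.4 to 52.1 and 312.8 subject-years and leave the conclusion unchanged. The upper-tail wording and the undefined lower limit at n = 0 are smaller defects in the same section. Because this is the sole interval for the primary safety variable, the correction is required.

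**What to change.** In SAP 8.1.4, replace equations (11) and (12) with:

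- LCL = 100 × χ²(0.025; 2n)/(2T), with LCL = 0 when n = 0
- UCL = 100 × χ²(0.975; 2(n+1))/(2T)

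Define T as the same sum of subject-years used in equation (10), including truncation at first occurrence for affected subjects. State that the quantiles are lower-tail (cumulative) probabilities and remove the reference to the upper tail.

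Then confirm that any EAIR program already written scales both limits by 100/T. The cost is about two lines of SAP text and, if the scaling is missing, about one line of code. No design element, data collection or point estimate changes.
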